8.4 Withdrawal of individual subjects

Subjects can leave the study at any time for any reason if they wish to do so without any consequences. The investigator can decide to withdraw a subject from the study for urgent medical reasons.

8.4.1 Specific criteria for withdrawal (if applicable)

N/A

8.5 Replacement of individual subjects after withdrawal

Enrolled subjects who decide to leave the study before the index procedure will be replaced by new subjects.

8.6 Follow-up of subjects withdrawn from treatment

Subjects who are withdrawn from the study will continue their follow-up in agreement with local practice.

8.7 Premature termination of the study

N/A

9. SAFETY REPORTING

9.1 Temporary halt for reasons of subject safety

In accordance with section 10, subsection 4 of the Medical Research Involving Human Subjects Act (*in Dutch: Wet Medisch-wetenschappelijk Onderzoek met Mensen, WMO*), the sponsor will suspend the study if there is sufficient ground that continuation of the study will jeopardize subject health or safety. The sponsor will notify the accredited METC without undue delay of a temporary halt including the reason for such an action. The study will be suspended pending a further positive decision by the accredited METC. The investigator will take care that all subjects are kept informed.

9.2 Adverse Events and Device Deficiencies

During the clinical investigation, undesired medical events can occur in participating patients, which are called adverse events (AEs) in the following. Furthermore, device deficiencies (DD) may also be observed. All AEs and DDs of the investigational device shall be assessed by the investigator and shall be documented and reported throughout the clinical investigation within the timelines defined below (Figure 9.2.1.). According to ISO 14155:2020 (third edition) events will be classified based on the definitions below. The investigator will report all reportable events to the sponsor without undue delay but not later than 3 calendar days after obtaining knowledge of the event (including assessment of causal relationship with device or investigational procedure). Reportable events are:

[figure not shown]
- a) Any SAE that has a causal relationship with the investigational device, the comparator, or the investigation procedure or where such causal relationship is reasonably possible
- b) Any DD that might have led to a SAE if appropriate action had not been taken, intervention had not occurred, or circumstances had been less fortunate
- c) Any new findings in relation to any event referred in point (a) and (b)

The sponsor will report reportable events through the web portal *ToetsingOnline* to the accredited METC that approved the protocol, within 2 calendar days of first knowledge for SAEs that result in death or are life threatening. All other SAEs will be reported within a period of maximum 7 calendar days after the sponsor has first knowledge of the SAE. All SAE will be reported and will be categorized as related to the device (SADE) or not.

The sponsor will report expedited unanticipated serious adverse device effects (USADEs) through the web portal *ToetsingOnline* to the METC. The expedited reporting of USADEs through the web portal *ToetsingOnline* is sufficient as notification to the competent authority. The expedited reporting will occur not later than 15 days after the sponsor has first knowledge of the adverse reactions. For fatal or life-threatening cases,

the term will be maximal 7 days for a preliminary report with another 8 days for completion of the report.

Figure 9.2.1. Adverse events flow

CCMO, version 2, 24 april 2021

9.2.1 Definition of Adverse Device Effects (ADE)

An adverse device effect (ADE) (see ISO 14155:2020 3.1) is an adverse event (AE) that is related to the use of an investigational medical device. This includes any AE resulting from insufficient or inadequate instructions for use or the deployment, implantation, installation, or operation, or any malfunctioning of the investigational medical device and any event resulting from use error or from intentional misuse of the investigational medical device. This includes comparator if the comparator is a medical device.

9.2.2 Definition of Adverse Events (AE)

An AE is defined (see ISO 14155:2020 3.2) as any untoward medical occurrence, unintended disease or injury, or untoward clinical signs (including abnormal laboratory findings) in subjects, users, or other persons whether or not related to the investigational medical device, and whether anticipated or unanticipated. This includes:

- Events related to the investigational medical device or the comparator
- Events related to the procedures involved
- For users or other persons, this definition is restricted to events related to the use of investigational medical devices or comparators

9.2.3 Causality Assessment

The relationship between the use of the investigational medical device (including the medical-surgical procedure) and the occurrence of each AE shall be assessed and categorized, considering the presence of confounding factors, such as concomitant medication and treatment, the natural history of the underlying disease, other concurrent illness, or risk factors. Each AE will be classified according to five different levels of causality. The investigator will use the following definitions to assess the relationship of the (serious) AE to the investigational medical device or procedures and the sponsor will review the investigators categorization:

- **Not related**: the relationship to the medical device or procedure can be excluded
- **Unlikely**: the relationship with the use of the medical device seems not relevant and/or the event can be reasonably explained by another cause, but additional information may be obtained.
- **Possible**: the relationship with the use of the investigational medical device is weak but cannot be ruled out completely. Alternative causes are also possible (e.g., an underlying or concurrent illness/clinical condition or/and an effect of another device, drug or treatment). Cases where relatedness cannot be

assessed, or no information has been obtained should also be classified as possible.

- **Probable**: the relationship with the use of the investigational medical device seems relevant and/or the event cannot be reasonably explained by another cause, but additional information may be obtained.
- **Causal relationship**: the (serious) event is associated with the investigational medical device or with procedures beyond reasonable doubt.

The investigators will distinguish between the AEs related to the investigational medical device and those related to the device procedures (any procedure specific to the investigational device). Procedure related events refers to the procedure related to the application of the investigational medical device only and therefore not to any other procedure for other devices and not to any other procedures or treatments applied later throughout the clinical investigation, for instance to treat (serious) AEs.

An AE can be related both to the procedure and the investigational medical device. Complications of procedures are considered not related if the said procedures would have been applied to the patients also in the absence of investigational medical device use or application.

9.2.4 Definition of Device Deficiency (DD)

Device deficiency (DD) (see ISO 14155:2020 3.19) is defined as inadequacy of a medical device with respect to its identity, quality, durability, reliability, usability, safety, or performance, including malfunctions, use errors and inadequacy in the information supplied by the manufacturer including labelling. This definition includes DD related to investigation medical device or the comparator.

DDs of the investigational medical device shall be documented throughout the study. DDs which caused an AE are reported on the respective adverse event form. In case the DD did not cause an adverse event, the provided DD form shall be used to document this “non-medical” event.

If a DD could have led to a SADE,

- If either suitable action had not been taken,
- If intervention had not been made, or
- If circumstances had been less fortunate,

The DD is classified as an DD with a SADE potential.

9.2.5 Definition of Serious Adverse Events (SAE)

AEs are classified as serious (see ISO 14155:2020 3.45) if one or more of the following consequences are fulfilled:

- a) Led to death
- b) Led to serious deterioration in the health of the subject, users, or other persons as defined by one or more of the following:
 - 1) A life-threatening illness or injury, or
 - 2) A permanent impairment of a body structure or a body function including chronic diseases, or
 - 3) In-patient or prolonged hospitalization, or
 - 4) Medical or surgical intervention to prevent life-threatening illness or injury, or permanent impairment to a body structure or a body function.
- c) Led to fetal distress, fetal death or a congenital abnormality or birth defect including physical or mental impairment.

Note: planned hospitalization for a pre-existing condition, or a procedure required by the clinical investigation plan (CIP), without serious deterioration in health is not considered a SAE. In-patient hospitalization is defined as at least one overnight stay (change of date) in a hospital. In case, a patient is only for some hours in the hospital (without change of date), this event will not be documented as serious, unless one or more other seriousness criteria are fulfilled.

9.2.6 Definition of Serious Adverse Device Effect (SADE)

An ADE (see ISO 14155:2020 3.44) that resulted in any of the consequences characteristic of a SAE is considered serious.

9.2.7 Definition of Unanticipated Serious Adverse Device Effects (USADE)

SADEs (see ISO 14155:2020 3.51) are defined as unanticipated if by their nature, incidence, severity, or outcome they have not been identified in the current risk assessment. These events must be reported to the sponsor immediately.

9.3 Annual safety report

An annual safety report will be submitted to the METC of the Erasmus MC.

9.4 Follow-up of adverse events

All SAEs will be followed until they have abated, or until a stable situation has been reached. Depending on the event, follow up may require additional tests or medical procedures as indicated, and/or referral to the general physician or a medical specialist. SAEs need to be reported till end of study within the Netherlands, as defined in the protocol.

9.5 Data Safety Monitoring Board (DSMB) / Safety Committee

A DSMB will not be established given low-risk character of the study and the well-established safety of the catheters. The principal investigator will be responsible for registering and reporting any ADEs, SADE or USADEs to the METC.

10. STATISTICAL ANALYSIS

10.1 Primary study parameters

The primary study parameter is the extent of the antral lesion size. The antral lesion size will be established using the parameters as detailed in Table 8.3.1.1. The antral lesion size will be described as absolute and relative measures. Absolute measures include nonablated LAPW, superior line, mid line, inferior line, circumferential antral lesion area, and posterior PV antral lesion area. Relative measures include the difference between the pre- and post-ablation maps regarding the absolute measures expressed as a percentage.

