3. STUDY DESIGN

3.1 Study design

Investigator-initiated, single-center, open label, prospective, single-arm study evaluating the 31 mm balloon size of the POLARx™ FIT cryoballoon. Before and after complete PVI, a 3-dimensional ultrahigh-density (UHDx) map will be created. The study population will consist of 20 patients undergoing a first PVI with a normal PV anatomy (exclusion of large common ostium or supernumerary veins as determined by a preprocedural CT-scan) in the Erasmus MC, Rotterdam, the Netherlands. Patients will be seen at the outpatient clinic 3 (blanking), 6 and 12 months after the index ablation to assess potential adverse events and recurrence of atrial arrhythmias. After the 1-year visit the study will end for the individual patient. The study flowchart is depicted in Figure 3.1.1.

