5.1.5 Confirmation of complete PVI

Electrical isolation of a PV is demonstrated by entrance and exit block. Entrance block is defined as the absence of local potentials inside the vein as assessed by the POLARMAP™ circular mapping catheter. Exit block is defined as absence of atrial capture while pacing from inside the vein with the POLARMAP™ circular mapping catheter. If a PV shows reconnection, repeat cryoablation will be performed with the goal of achieving electrical isolation. This can be performed with the 28 mm or 31 mm balloon size per operator discretion. Complete PVI is defined as electrical isolation of all PVs. After complete PVI, post-ablation UHDx mapping will be performed.

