5.1.6 Post-ablation UHDx mapping

After achieving complete PVI, the 64-pole mini-basket mapping catheter will be introduced through the POLARSHEATH for repeat mapping. Repeat mapping will be preferentially performed in sinus rhythm with prior cardioversion of AF if required. There will be no specified waiting time before remapping. LA voltage maps will be constructed with special point density in the antra of PVs. Post-ablation LA lesion surface area will be assessed as previously described.²³ The key parameters that will be collected are described in the Methods section. If conduction gaps or PV reconnections are found during UHDx mapping, the mapping catheter will be replaced by the POLARx™ cryoablation catheter and additional ablations will be performed to achieve complete PVI. Another UHDx map will be constructed after re-isolation.

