8. METHODS

8.1 Study parameters/endpoints

8.1.1 Main study parameter/endpoint

- Extent of antral lesion size (continuous variable) directly after cryoablation with a 31 mm balloon size POLARx™ FIT cryoablation catheter. Measures of antral lesion size are described in paragraph 8.3.1. and Table 8.3.1.1.

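### Does section 10.1 leave the choice of post-ablation map open, and ask for percentages that cannot be computed?

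*Combined protocol and SAP*

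**What the plan says.** Section 10.1 takes its parameters from Table 8.3.1.1 and splits them into absolute and relative measures. The absolute list reads: "Absolute measures include nonablated LAPW, superior line, mid line, inferior line, circumferential antral lesion area, and posterior PV antral lesion area". The relative measures are then defined: "Relative measures include the difference between the pre- and post-ablation maps regarding the absolute measures expressed as a percentage".

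On the timing of the post-ablation map:

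- 3.1: "Before and after complete PVI, a 3-dimensional ultrahigh-density (UHDx) map will be created".
- 5.1.5 defines complete PVI as isolation of every vein, and adds: "After complete PVI, post-ablation UHDx mapping will be performed".
- 5.1.6 opens: "After achieving complete PVI, the 64-pole mini-basket mapping catheter will be introduced through the POLARSHEATH for repeat mapping".
- 5.1.6 also covers a failed check. Its condition is "If conduction gaps or PV reconnections are found during UHDx mapping". In that case further ablation is given with the aim of reaching complete PVI, and then: "Another UHDx map will be constructed after re-isolation".
- 8.1.1 words the endpoint as "Extent of antral lesion size (continuous variable) directly after cryoablation with a 31 mm balloon size".

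Table 8.3.1.1 has a single post-ablation column. It marks both columns for the non-ablated posterior wall (LAPW) area and for the superior, middle and inferior lines. The pre-ablation column has a dash for the left and right circumferential areas and for the posterior antral area.

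**The concern.** A re-isolated patient has two post-ablation maps, and neither 8.3.1, the table nor 10.1 says which one fills the column. The first map may show an incomplete lesion. The second shows it after extra applications. Section 5.1.6 describes even the first map as made after complete PVI, and the endpoint wording in 8.1.1 could be taken to mean the map made soonest after ablation. If the choice were truly open, it could be made with both sets of measurements in view. The plan sets no blinding for map measurement: 8.2 is marked not applicable, and 8.3.2 blinds only the venogram observers. The absolute antral areas, which the primary objective concerns, would be affected as well as the percentages.

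The second worry is that 10.1, taken literally, asks for a percentage change in two area types that have no baseline. If the pre-ablation lesion area is set to zero, the ratio is a division by zero.

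**Working it through.** **Which map.** The sections are read in the order of the procedure.

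1. 5.1.5 sets the state to be reached: all veins isolated.
2. 3.1 and 5.1.5 place the study map after that state.
3. 5.1.6 introduces the mapping catheter once isolation has been confirmed with the circular catheter. If the detailed map then shows a gap or reconnection, 5.1.6 describes the extra ablation as the means of achieving complete PVI. The protocol therefore treats that patient as not yet there.
4. For that patient only the map made after re-isolation follows complete PVI. It is also the last map.
5. The timing phrase in 8.1.1 does not contradict this. The last map also follows directly on a cryoapplication. The phrase contrasts naturally with the later voltage map that 5.1.7 prefers at a repeat procedure.
6. Balloon size does not separate the maps. 5.1.4 lets the operator choose the size for applications after the first, before any post-ablation map exists, and 5.1.5 allows either size for a reconnected vein. Either map may therefore include 28 mm applications.

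**Which measures have a percentage.** 10.1 lists six measure types. Table 8.3.1.1 pairs four of them, the LAPW area and three lines (4/6 = 67%). The circumferential and posterior antral areas are post-ablation only.

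**Scale of the map choice.** The plan gives no figure to reproduce; 4.4 states N = 20 and the SDs but no target width.

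- Inputs from 4.4, which are pulsed field data and not from this balloon: left 20.5 ± 3.8 cm², right 25.5 ± 5.7 cm².
- 95% half-width = t(0.975, 19) × SD/√20. Left: 2.093 × 3.8/4.472 = 1.78 cm². Right: 2.093 × 5.7/4.472 = 2.67 cm².
- If k of 20 patients have two maps that differ by d cm², the mean shifts by k × d/20.

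Neither k nor d is in the documents, so both are assumed:

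| d (cm²) | k = 1 | k = 2 | k = 4 |
|---|---|---|---|
| 1 | 0.05 | 0.10 | 0.20 |
| 2 | 0.10 | 0.20 | 0.40 |
| 4 | 0.20 | 0.40 | 0.80 |
| 10.25 (20.5/2, left) | 0.51 | 1.03 | 2.05 |
| 12.75 (25.5/2, right) | 0.64 | 1.28 | 2.55 |

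The last two rows are extreme cases in which one vein's whole share of a side is missing from the first map, with an even split between the two veins. Even then the shift equals the half-width only at k = 1.78 × 20/10.25 = 3.5 patients (left) or 2.67 × 20/12.75 = 4.2 patients (right). A local gap would be expected to give a much smaller d.

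For the chance that the case arises at all, 1 − (1 − q)^20 at assumed per-patient rates q of 2%, 5%, 10% and 20% gives 33%, 64%, 88% and 99%.

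**The case for a change.** The strongest case for a change is that the protocol itself foresees two maps, and at quite modest assumed rates at least one such patient among 20 is likely. The endpoint is primary, the measurement is unblinded, and one sentence would close the gap. The last map is also only an inference, since 5.1.6 uses the same complete-PVI condition for the first map.

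Part of this stands. No sentence in 8.3.1 or 10.1 names the map, and the percentage wording is broader than the table. The inference is a firm one, however. The opening of 5.1.6 refers to isolation as judged by the circular catheter, and the same section then treats a gap on the detailed map as showing that the goal has not been met.

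The worry about choosing after the fact carries little weight here. The study has one arm, and its primary analysis is descriptive, without a hypothesis test or threshold that a favourable choice could cross. First-map values might not be a usable alternative in any case. Gaps are found while mapping is under way, and the protocol does not say that this map is finished before the catheters are exchanged.

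**Conclusion.** No change follows. On the map, 10.1 is silent, but an analyst who reads 3.1, 5.1.5 and 5.1.6 together would use the last map, made after confirmed isolation of all veins. A written rule would record what would be done anyway. On the percentage, the fault is loose wording. Table 8.3.1.1 shows that a pre/post percentage exists for four of the six measure types, and the antral areas are reported in cm². No result, test or conclusion changes.

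The size of the map question cannot be established from the documents. The number of remapped patients is not given and may be zero, and the difference between maps is assumed throughout. With differences of 1 to 4 cm² in one or two patients, the mean moves by 0.05 to 0.40 cm², against half-widths of 1.78 and 2.67 cm². Those half-widths assume that the pulsed field SDs in 4.4 carry over to this balloon. The larger shifts in the table need several patients who each lack a whole vein's share of the lesion, and nothing in the documents suggests that.

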10.2 Secondary study parameters

The secondary study parameters are the proportion of grade 4 occlusion and the single shot success rate. Both will be determined per PV and expressed as frequency and percentage (N, %). The difference in the proportion of grade 4 occlusion between the 28 mm and 31 mm balloon size will be compared using the McNemar test for paired nominal data.

10.3 Other study parameters

N/A

10.4 Interim analysis (if applicable)

N/A

11. ETHICAL CONSIDERATIONS

11.1 Regulation statement

The study will be conducted according to the principles of the Declaration of Helsinki (version 2013), ISO 14155: 2020, WMO and other regional and local laws.

11.2 Recruitment and consent

Patients who are referred to the study center for a PVI are always seen by a physician on a dedicated outpatient clinic to inform them on the procedure, efficacy, and risks of a PVI. If the patient is a suitable patient for a PVI with a cryoballoon and the patient gives consent for the procedure, they are considered potential study candidates. If they fulfil the in- and exclusion criteria as defined in chapter 4, then they will be approached by a member of the study team (not treating physician) to explain the study and obtain informed consent if the patient is eligible and willing to participate in the study. Informed consent will be obtained and documented in writing before a subject is enrolled in the clinical study. It is the responsibility of the investigator to ensure that a written informed consent is obtained from the subject (or legally acceptable representative) before any activity or procedure is undertaken that is not part of routine care.

11.3 Objection by minors or incapacitated subjects (if applicable)

N/A

11.4 Benefits and risks assessment, group relatedness

The hypothesis is that the larger balloon size of POLARx™ FIT cryoablation catheter will result in a larger antral lesion size. This may have a beneficial effect by reducing the risk of recurrence of AF after the index procedure. In general, cryoballoon procedures are associated with less periprocedural risks compared to PVI using RF. It is expected that the larger balloon size (31 mm versus 28 mm) will not result in a significant increase in periprocedural complications. Catheter handling will not change due to the larger balloon size. One of the most common complications due to CB procedures is right-sided PNP. It is expected that a larger balloon size will have a beneficial effect on the risk of PNP because the larger balloon size will prevent placement of the CB too deep in the right-sided PVs. By having a more antral position of the CB the risk of PNP is decreased.

